#### Net head acceleration measurement:

For each loading condition, net head acceleration will be measured using a kinematic camera system in a similar manner as previously described by our group. Subjects will wear optoelectronic markers (infrared emitting diodes) to allow tracking of head position in space and relative to the torso. Signal processing will be performed in a similar manner as previously described by our group to calculate head accelerations. For the checking/blocking and soccer heading tasks, subjects will wear a thin force sensor on their shoulder (for checking/blocking) or forehead (for soccer heading) to identify the time of impact between their shoulder/forehead and the punching bag/soccer ball, respectively. In the unlikely event that head kinematics patterns are not sufficiently stereotyped under a given loading condition for between-subject comparisons of AUC for the net head acceleration vector, which does not directly account for directionality, then we would decompose the net acceleration vector into its individual linear and angular components. Participants will also wear a second inertial measurement unit (body-worn sensor) on their heads to provide redundant head acceleration data as a back-up in the unlikely event that the kinematic camera data cannot be adequately resolved. Additionally, if the force sensing resistor used to identify the onset of head acceleration during the checking/blocking and soccer heading tasks unexpectedly fails for a given trial, we would alternatively use a similar technique to the one we have previously employed to identify the onset of head acceleration from the kinematic dataset via a trailing window.

**Methodology for measuring cervical muscle attributes:** Given that muscular adaptation to resistance exercise results in strength gains attributable to both improved neuromuscular recruitment and muscle hypertrophy, we will assess neck strength as well as cervical muscle volume and neuromuscular activation.

## **Neck strength**

Neck strength will be measured both in terms of the peak force/moment and rate of force/torque development in cervical flexion, extension, axial rotation, and lateral flexion using a customized laboratory testing apparatus similar to that previously described by [name]. Measured force values will be converted to moments, in N·m, by multiplying each force value by the neck's estimated moment arm.

#### **Cervical muscle volume**

The total cervical muscle volume will be measured using magnetic resonance imaging (MRI) without contrast in a similar manner as previously described by [name]. The volume of individual cervical muscles will be calculated by integrating the cross sectional areas (CSA's) across slices multiplied by slice center-to-center spacing and total cervical muscle volume will be calculated as the sum of volumes of the individual muscles.

Estimated cervical muscle volume will also be calculated at each assessment using a predictive regression equation developed by [name] lab, which has been shown to accurately account for 87% of the variance in MRI-based total cervical muscle volume based on overall neck circumference and sex. We will further refine this regression-based estimate by incorporating the sonographic anatomical cross-sectional areas (CSA's) of key cervical muscles measured at each assessment time point, with validation of the expanded model using our MRI-based cervical muscle volume measurements. We will assess the sternocleidomastoid (SCM), upper trapezius (TRAP), splenius capitis (SPL), and semispinalis capitis (SEMI) muscles, which we have previously studied with acceptable test-retest reliability (intra-class correlation coefficients, ICC= .91 to ICC= .99) and validity as compared to criterion-standard MRI CSA measurements (R= .76 to R= .97). In the unlikely event that we are unable to adequately predict total cervical muscle volumes using [name] regression equation, we would alternatively assess cervical muscle hypertrophy using total neck circumference and the sonographic anatomical CSA measurements of the SCM, TRAP, SPL, and SEMI muscles.

#### **Cervical muscle activation**

We will quantify neuromuscular recruitment of the cervical muscles in terms of agonist muscle activation and antagonist muscle inhibition, using a similar surface electromyography (sEMG) protocol as during our pilot neck strengthening study. Briefly, after standard skin preparation sEMG electrodes placed over the SCM, TRAP, SPL, and SEMI muscles will measure muscle activation during maximum voluntary contraction and under each loading condition. Raw sEMG data will be normalized with respect to each muscle's maximum amplitude, with agonist muscle activation and antagonist muscle inhibition calculated as the mean normalized sEMG amplitude (percentage of maximum) of the agonist and antagonist muscles during maximum voluntary contraction in each plane of motion. The mean activation level of each cervical muscle will also be measured during the loading tasks, allowing assessment of agonist activation and antagonist inhibition, as well as agonistantagonist co-contraction and muscle activation onset latencies during loading.

#### **Estimated cervical muscle stiffness**

We will estimate cervical muscle stiffness by imposing cervical muscle volume, head kinematics, and sEMG data onto [name] multi-body dynamic neck model in a similar manner as previously used to accurately estimate joint stiffness in an elbow model.

All results will be collected by the study team through the conduct of this research study and are for research purposes only. As such, no medical record review will be performed and no study results will routinely be reported to participants. Individual participant or parent/guardian requests for study results will be considered by the PI on a case-by-case basis and requested information will be provided at the discretion of the PI when feasible for the study team to do so.

## 8.2 SAFETY AND OTHER ASSESSMENTS

Potential participants meeting any exclusion criteria (See Section 5.2), either during the initial phone screen or the final in-person screening assessment which includes a brief screening physical examination, may potentially be at slightly increased risk for injury as a result of study participation and so out of caution will be excluded from study participation.

Potential participants with disqualifying findings on the screening physical examination (and their parent/guardian if they are a minor) will be notified verbally at the time of the screening examination, and will subsequently be notified in writing, of the specific disqualifying physical exam finding. They will be advised to follow up with their primary care physician.

Participants will be asked at the beginning of each study-associated exercise and testing session whether they have experienced any AE's as described below in Section 8.3.4. Participants will also be observed by the study team during each study visit for AE's.

Any moderate or severe AE's will be reported to the PI, or his designee, for determination of the need for medical follow up. If immediate emergent medical care is deemed necessary 9-1-1 will be called. If urgent, non-immediate, medical care is deemed necessary the participant will be referred to a local Emergency Department or Urgent Care Center via their own private transportation. If non-urgent medical care is deemed necessary, the participant will be referred to their own physician's office. If no medical care is deemed necessary, the participant will be advised to monitor their condition and contact their own physician if their condition worsens prior to their next study visit.

All study MRI's will be reviewed by the Study Radiologist for quality control purposes, as well as to screen for incidental findings of clinical significance. If incidental clinically significant findings are identified, the Study Radiologist will note them in the research MRI report and will alert the PI (or his designee if he is unavailable) to their presence. The PI (or his designee) will subsequently contact the subject (and their parent/guardian if they are a minor) by phone to notify them of the incidental finding and advise them to follow up with their primary care physician. In addition, a written notification of the incidental finding, including a copy of the research MRI report, will be sent to the subject, as well as to their primary care physician providing them medical care if this is their preference.

## 8.3 ADVERSE EVENTS AND SERIOUS ADVERSE EVENTS

# 8.3.1 DEFINITION OF ADVERSE EVENTS (AE)

Adverse event means any untoward medical occurrence associated with the use of an intervention in humans, whether or not considered intervention-related (21 CFR 312.32 (a)).

Note: delayed onset muscle soreness is a normal, anticipated occurrence following resistance exercise training and is therefore not considered an AE for the purposes of this study.

## 8.3.2 DEFINITION OF SERIOUS ADVERSE EVENTS (SAE)

An adverse event (AE) or suspected adverse reaction is considered "serious" if, in the view of the investigator or his designee, it results in any of the following outcomes: death, a life-threatening adverse event, inpatient hospitalization or prolongation of existing hospitalization, a persistent or significant incapacity or substantial disruption of the ability to conduct normal life functions, or a congenital anomaly/birth defect. Important medical events that may not result in death, be life-threatening, or require hospitalization may be considered serious when, based upon appropriate medical judgment, they may jeopardize the participant and may require medical or surgical intervention to prevent one of the outcomes listed in this definition. Examples of such medical events include allergic bronchospasm requiring intensive treatment in an emergency room or at home, blood dyscrasias or convulsions that do not result in inpatient hospitalization, or the development of drug dependency or drug abuse.

# 8.3.2.1 SEVERITY OF EVENT

For adverse events (AEs) not included in the protocol defined grading system, the following guidelines will be used to describe severity.

- **Mild** Events require minimal or no treatment and do not interfere with the participant's daily activities.
- **Moderate** Events result in a low level of inconvenience or concern with the therapeutic measures. Moderate events may cause some interference with functioning.
- Severe Events interrupt a participant's usual daily activity and may require systemic drug therapy or other treatment. Severe events are usually potentially life-threatening or incapacitating. Of note, the term "severe" does not necessarily equate to "serious".

# 8.3.2.2 RELATIONSHIP TO STUDY INTERVENTION

All adverse events (AEs) will have their relationship to study intervention assessed by the PI, or his designee, based on temporal relationship and his/her clinical judgment. The degree of certainty about causality will be graded using the categories below. The study-assigned exercise program will always be considered suspect.

- **Definitely Related** There is clear evidence to suggest a causal relationship, and other possible contributing factors can be ruled out. The clinical event occurs in a plausible time relationship to study intervention administration and cannot be explained by concurrent disease or other exposure/event (e.gs., drug, chemical, toxin, pathogen, activity, environmental factor, traumatic event). The response to withdrawal of the study intervention (dechallenge) should be clinically plausible. If medically appropriate, a rechallenge procedure may be employed, with a positive response to rechallenge considered as confirmation of definite relatedness.
- **Probably Related** There is evidence to suggest a causal relationship, and the influence of other factors is unlikely. The clinical event occurs within a reasonable time after administration of the study intervention, is unlikely to be attributed to concurrent disease or other or other exposure/event, and follows a clinically reasonable response on withdrawal (dechallenge). Rechallenge information is not required to fulfill this definition.
- **Potentially Related** There is some evidence to suggest a causal relationship (e.g., the event occurred within a reasonable time after administration of the trial medication). However, other factors may have contributed to the event (e.g., the participant's clinical condition, other concomitant events). Although an AE may rate only as "possibly related" soon after discovery, it

can be flagged as requiring more information and later be upgraded to "probably related" or "definitely related", as appropriate.

- Unlikely to be related A clinical event whose temporal relationship to study intervention administration makes a causal relationship improbable (e.g., the event did not occur within a reasonable time after administration of the study intervention) and in which other disease or exposure/event provides plausible explanations (e.g., the participant's clinical condition, other concomitant treatments).
- Not Related The AE is completely independent of study intervention administration, and/or evidence exists that the event is definitely related to another etiology. There must be an alternative, definitive etiology documented by the clinician.

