## **6** STUDY INTERVENTION

#### 6.1 STUDY INTERVENTION(S) ADMINISTRATION

#### 6.1.1 STUDY INTERVENTION DESCRIPTION

The study intervention is participation in a supervised exercise program. Participants will perform two exercise sessions per week, with at least one day between sessions. All participants will perform a standardized set of general resistance exercises targeting the chest, shoulders, back, upper and lower extremities, and core. In addition, those participants allocated to the high intensity neck strengthening group will also perform manual resistance exercises in sagittal plane flexion and extension, coronal plane lateral flexion in both directions, and axial plane rotation in both directions, as well as dumbbell shoulder shrugs.

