# 8.3.3 TIME PERIOD AND FREQUENCY FOR EVENT ASSESSMENT AND FOLLOW-UP

The occurrence of an adverse event (AE) or serious adverse event (SAE) may come to the attention of study personnel during study visits or if communicated to the study team between visits. The study team will not prompt participants for any specific solicited AE's, but will ask about unsolicited AE's at each study visit using the following general question: "Have you noticed any new illness, injury, or other health-related concerns since your last study visit?"

All AEs including local and systemic reactions not meeting the criteria for SAEs will be captured on the appropriate case report form (CRF). Information to be collected includes event description, time of onset, clinician's assessment of severity, relationship to study intervention (assessed by the PI or his designee with the training and authority to make a diagnosis), and date of resolution/stabilization of the event. All AEs occurring while on study must be documented appropriately regardless of relationship. All AEs will be followed to adequate resolution.

Any medical condition that is present at the time that the participant is screened will be considered as baseline and not reported as an AE. However, if the study participant's condition deteriorates at any time during the study, it will be recorded as an AE.

Changes in the severity of an AE will be documented to allow an assessment of the duration of the event at each level of severity to be performed. AEs characterized as intermittent require documentation of onset and duration of each episode.

The study coordinator or project manager will record all reportable events with start dates occurring any time after informed consent is obtained until 7 (for non-serious AEs) or 30 days (for SAEs) after the last day of study participation. At each study visit, the investigator will inquire about the occurrence of AE/SAEs since the last visit. Events will be followed for outcome information until resolution or stabilization.

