## 8.3.4 ADVERSE EVENT REPORTING

AE and SAE reporting to IRBMED will occur per IRBMED standard reporting guidelines. Reporting to the DSMB will occur in conjunction with annual DSMB meetings as scheduled per the DSMB Charter. Additionally, any serious adverse event deemed possibly, probably, or definitely related to study procedures, or were IRBMED standard reporting guidelines otherwise necessitate more immediate reporting, will be reported to the DSMB on the same schedule as reports to IRBMED or within 14 calendar days of identification, whichever occurs first.

Note that if a series of related, expected AE's of moderate severity appear to be occurring at a frequency greater than previously known or expected, the study team will report this to IRBMED and the DSMB within 14 calendar days of identifying the trend.

Unrelated, non-serious AE's (expected or unexpected) will not be reported to IRBMED or the DSMB unless there appears to be a trend of events occurring at a frequency greater than previously known or expected, in which case the study team will also report this trend to IRB-MED as well as the DSMB within 14 calendar days of identifying the trend.

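### AE causality is graded only against the exercise programme, so injuries from the laboratory tests can be classed as unrelated, and the reporting rules do not agree on what an event must be related to

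*Combined protocol and SAP*

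**What the plan says.** Section 8.3.2.2 sets the grading rule: "All adverse events (AEs) will have their relationship to study intervention assessed by the PI, or his designee". It adds: "The study-assigned exercise program will always be considered suspect". No laboratory procedure is mentioned there. Section 8.3.3 lists what is captured for each AE, including "relationship to study intervention (assessed by the PI or his designee with the training and authority to make a diagnosis".

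Section 6.1.1 fixes the meaning of the term: "The study intervention is participation in a supervised exercise program". The laboratory assessments are described separately, in Section 8.1.

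Under the scale, Not Related applies where "evidence exists that the event is definitely related to another etiology", with the alternative cause documented by the clinician.

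The reporting rules use other wording. Section 8.3.4 expedites to the DSMB "any serious adverse event deemed possibly, probably, or definitely related to study procedures". It also says "Unrelated, non-serious AE's (expected or unexpected) will not be reported to IRBMED or the DSMB", with an exception for a trend. Section 8.3.5 sets 7- and 14-day limits for related, unexpected SAEs without naming what they are related to. Section 9.4.3 summarises AEs by relatedness, also without an object.

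**The concern.** The medical harms that Section 2.3.1 names come largely from the assessments: neck pain and headache from direct loading, checking and heading; chest, back or shoulder pain from the punching bag; fainting during ultrasound; minor burns and skin irritation. The only harm it names for the exercise sessions is muscle soreness, and Section 8.3.1 removes that from AE reporting: "delayed onset muscle soreness is a normal, anticipated occurrence following resistance exercise training and is therefore not considered an AE". The scale therefore points at the component with no listed harm that can become an AE. It is silent on the components that do have such harms.

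The relatedness grade feeds both the routine reports to the IRB and DSMB and the safety table. If it does not cover the tests, neither output can show whether impacts delivered to participants aged 13 to 19 caused injury.

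**Working it through.** No arithmetic settles whether the rule is wrong; the check is to compare the sections and follow a test-caused injury through them.

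**Step 1: what relatedness refers to in each place**

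| Section | What it governs | Related to what |
|---|---|---|
| 8.3.2.2 | causality grade | study intervention (exercise, by 6.1.1) |
| 8.3.3 | item recorded for each AE | study intervention |
| 6.2 | why the PI or designee is unblinded | the study |
| 8.3.4 | SAEs expedited to the DSMB | study procedures |
| 8.3.4 | non-serious AEs not reported | not stated |
| 8.3.5 | 7- and 14-day limits | not stated |
| 8.4.1 | unanticipated problems | participation in the research, including its procedures |
| 9.4.3 | safety table | not stated |
| 9.4.5 | temporary suspension | the study; acts on the protocol portion deemed causal |

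Only the first two rows describe a grade that is recorded. Expectedness (8.3.2.3) is judged against Section 2.3.1, which does cover the tests. The same headache can therefore be expected from a test and Not Related on the scale.

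**Step 2: a non-serious injury clearly caused by a test**

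1. The cause is the test, not the exercise programme, so the literal grade is Not Related.
2. Section 8.3.4 then keeps it from the IRB and DSMB unless a trend appears. Had it been graded related, it would have fallen under the general rule of reporting at the annual DSMB meeting.
3. Section 2.3.1 classes every harm it names as non-serious, so the SAE safeguard in 8.3.4 does not reach these events.
4. An unexpected event that suggests greater risk could still qualify as an unanticipated problem under 8.4.1. But 8.4.2 sends such events to 8.3.5 and 8.3.6. The first gives time limits for SAEs only, and the second concerns informing participants. A non-serious one has no stated limit.
5. In the 9.4.3 table the event is counted as unrelated.

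**Step 3: an unexpected SAE clearly caused by a test**

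- *DSMB, under 8.3.4:* it is reported on the IRB schedule or within 14 calendar days, whichever is first, provided someone judges it related to study procedures. The recorded grade does not supply that judgement.
- *Section 8.3.5, if related means any study activity:* 7 days to the IRB and DSMB if fatal or life-threatening, otherwise 14.
- *Section 8.3.5, if related means the 8.3.2.2 grade:* the unrelated route, meaning standard IRB guidelines and scheduled DSMB meetings.

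Because 8.3.4 still applies, the two readings of 8.3.5 differ for the DSMB by at most 14 − 7 = 7 days for a fatal or life-threatening event, and by 14 − 14 = 0 days for any other SAE. This treats identification and awareness of the event as the same date. For the IRB, the choice is between a stated limit and standard guidelines that the documents do not reproduce.

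**Step 4: suspension**

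Section 9.4.5 asks whether an unexpected SAE is study-related and suspends the portion of the protocol deemed responsible. This covers the tests and does not depend on the 8.3.2.2 grade.

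**The case against.** The strongest reply is that the protocol already protects against the serious cases. A reader might infer from the grading rule that test-caused injuries drop out of expedited reporting. The documents do not support that. Section 8.3.4 expressly covers SAEs related to study procedures, and Section 8.4.1 covers problems caused by research procedures. A single non-serious AE has no 7- or 14-day AE route to lose, whatever its grade, and a trend is reportable within 14 days even among unrelated events. A reader might also infer that the grade decides whether activities are suspended. Section 9.4.5 sets its own test, so it does not. These parts of the reply stand.

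Second, the wording of 6.2 and the expectedness rule suggest that relatedness was meant study-wide. If related meant exercise only, the class of related, expected, moderate AEs in 8.3.4 would be almost empty. This is fair evidence of intent, but it shows that the definition and the recorded item do not match that intent.

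Third, Not Related requires a documented alternative cause, and exercise is always suspect, so the grade is not automatic and the source record should show the procedure. That stands in part. The 9.4.3 summary counts grades, not narratives. If the investigator instead grades a test injury as related, the scale attributes it to exercise. The table cannot show which happened.

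Fourth, the AE form and the Manual of Procedures are not among the documents, and the list in 8.3.3 may not be complete. A further field may exist. The protocol text would still need to agree with it.

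**Conclusion.** The point holds as a moderate defect in safety classification and reporting. As written, the only scale and the only listed relatedness item refer to exercise. A non-serious test-caused injury can therefore be omitted from routine IRB and DSMB reports and counted as unrelated. For a test-caused SAE, the DSMB and suspension routes remain, and the remaining problem is the ambiguity in 8.3.5.

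The number of events affected cannot be estimated. Counting the risk-bearing components in 2.3.1, or the impacts each athlete receives, might look like a measure of size, but those counts describe exposure and not misclassification.

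The conclusion assumes that the 6.1.1 definition governs the term in 8.3.2.2 and 8.3.3, and that no unseen form or manual adds a second attribution. The documents do not show how AEs have been graded in practice, so no actual misreporting is claimed.

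**What to change.** 1. In 8.3.2.2, and on the AE form described in 8.3.3, record relatedness separately to the exercise programme and to study assessments, naming the procedure.
2. State in 8.3.4, 8.3.5, 9.4.3 and 9.4.5 that related means related to either. Reconcile 8.3.4 and 8.3.5 so that a test-caused SAE has one unambiguous time limit, and correct the cross-reference in 8.4.2 so that it covers non-serious AEs.
3. Tabulate the two attributions separately in 9.4.3.
4. Check AEs already recorded and re-grade any that were judged against exercise alone.
5. As a clerical matter, use one label: the scale is headed *Potentially Related*, while 8.3.4 says *possibly*.

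The cost is protocol wording, one added form field and a review of existing AEs by the PI or designee who already grades them. No extra visits or staff are needed.
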